5.3.2.8 Pancreatic events

Symptoms of abdominal pain associated with elevations of amylase and lipase, suggestive of pancreatitis, have been associated with the administration of atezolizumab. The differential diagnosis of acute abdominal pain should include pancreatitis. Appropriate work-up should include an evaluation for ductal obstruction, as well as serum amylase and lipase tests.

Table 7: Management guidelines for Pancreatic events including pancreatitis

Severity	Management
	•
Grade 2	Amylase and/or lipase >1.5-2.0xULN:
amylase/lipase elevation	Continue atezolizumab.
Cicvation	 Monitor amylase and lipase weekly.
	 For prolonged elevation (e.g., > 3 weeks), consider treatment with 10 mg/day oral prednisone or equivalent.
	Asymptomatic with amylase and/or lipase >2.0-5.0xULN:
	Treat as grade 3
	•
Grades 3 and 4	Withhold atezolizumab for up to 12 weeks. ^a
amylase/lipase elevation	Refer patient to gastrointestinal specialist.
	 Monitor amylase/lipase every other day, and consider oral prednisone 1- 2 mg/kg/day or equivalent if no improvement.
	 Atezolizumab may be resumed if the event resolves to Grade 0 or Grade 1

within 12 weeks b

- Permanently discontinue atezolizumab and contact the principal investigator if event does not resolve to Grade 1 or better within 12 weeks.
- Permanently discontinue atezolizumab for recurrent Grade 3 or 4 amylase/lipase elevations and contact the principal investigator c

Immune-related pancreatitis, Grade 2 or 3

- Withhold atezolizumab for up to 12 weeks after event onset.^a
- Refer patient to gastrointestinal specialist.
- Initiate treatment with 1–2 mg/kg/day intravenous methylprednisolone or equivalent and convert to 1–2 mg/kg/day oral prednisone or equivalent upon improvement.
- Resume atezolizumab if event resolves to Grade 1 or better within 12 weeks.
- Permanently discontinue atezolizumab and contact the Medical Monitor if event does not resolve to Grade 1 or better within 12 weeks.
- For recurrent events, permanently discontinue atezolizumab and contact the Medical Monitor.

Immune-related pancreatitis, Grade 4

- Permanently discontinue atezolizumab and contact the principal investigator °
- · Refer patient to gastrointestinal specialist.
- Initiate treatment with 1–2 mg/kg/day intravenous methylprednisolone or equivalent and convert to 1–2 mg/kg/day oral prednisone or equivalent upon improvement.
- If event does not improve within 48 hours after initiating corticosteroids, consider adding an immunosuppressive agent.
- If event resolves to Grade 1 or better, taper corticosteroids over ≥ 1 month.

IV=intravenous; PO=orally.

a Atezolizumab may be withheld for a period of time beyond 12 weeks to allow for corticosteroids to be reduced to \leq 10 mg/day oral prednisone or equivalent. The acceptable length of the extended period of time must be based on the investigator benefit-risk assessment and in alignment with the protocol requirement fir duration of treatment and documented by the investigator. The Medical Monitor is available to advise as needed

b If corticosteroids have been initiated, they must be tapered over \geq 1 month to \leq 10 mg/day oral prednisone or equivalent before atezolizumab can be resumed.

c Resumption of atezolizumab may be considered in patients who are deriving benefit and have fully recovered from the immune-related event. Patients can be rechallenged with atezolizumab only after approval has been documented by both the investigator (or an appropriate delegate) and the sponsor.

5.3.2.9 Dermatologic Events

The majority of cases of rash reported with the use of atezolizumab were mild in severity and self-limited, with or without pruritus. Although uncommon, cases of severe cutaneous adverse reactions such as Stevens-Johnson syndrome and toxic epidermal necrolysis have been reported with atezolizumab. A dermatologist should evaluate persistent and/or severe rash or pruritus. A biopsy should be considered unless contraindicated.

18/12/2023 version 6.1 Confidential

Page 59 of 117

Table 8: Management Guidelines for Dermatologic Events

Severity	Management
Grade 1	Continue atezolizumab.
	 Consider topical steroids and/or other symptomatic therapy (e.g., antihistamines).
Grade 2	Continue atezolizumab.
	Consider dermatologist referral.
	Administer topical corticosteroids.
	Consider higher potency topical corticosteroids if event does not improve.
	 If unresponsive to topical corticosteroids, consider oral prednisone 0.5 mg/kg/day.
Grade 3	Withhold atezolizumab.
	Refer patient to dermatologist.
	 Initiate treatment with 10 mg/day oral prednisone or equivalent, increasing dose to 1–2 mg/kg/day if event does not improve within 48–72 hours.
	 Restart atezolizumab if event resolved to Grade 1 or better within 12 weeks. a, b,
	 Permanently discontinue atezolizumab and contact the principal investigator if event does not resolve to Grade 1 or better within 12 weeks.^{a, b, c}
Grade 4	Permanently discontinue atezolizumab.and Contact the Medical Monitor ^c
Stevens- Johnson	Additional guidance for Stevens-Johnson syndrome or toxic epidermal necrolysis:
syndrome or toxic epidermal necrolysis (any grade)	 Withhold atezolizumab or atezolizumab-tiragolumab for suspected Stevens- Johnson syndrome or toxic epidermal necrolysis.
	 Confirm diagnosis by referring patient to a specialist (dermatologist, ophthalmologist, or urologist as relevant) for evaluation and, if indicated, biopsy.
	 Follow the applicable treatment and management guidelines above.
	 If Stevens-Johnson syndrome or toxic epidermal necrolysis is confirmed, permanently discontinue atezolizumab or atezolizumab-tiragolumab.
	•

a If corticosteroids have been initiated, they must be tapered over ≥1 month to ≤10 mg/day oral prednisone or equivalent before atezolizumab can be resumed.

Severe Cutaneous Adverse Reactions (SCARs), including SJS, TEN, acute generalized exanthematous pustulosis and DRESS/DIHS General instructions:

- 1. Discontinue treatment and monitor closely for improvement, regardless of grade.
- 2. Rule out any other etiology of the skin problem, such as an infection, an effect of another drug, or a skin condition linked to another systemic disease.

Atezolizumab may be withheld for a period of time beyond 12 weeks to allow for corticosteroids to be reduced to ≤10 mg/day oral prednisone or equivalent. The acceptable length of the extended period of time must be agreed upon by the investigator and the Medical Monitor.

^c Resumption of atezolizumab may be considered in patients who are deriving benefit and have fully recovered from the immune-related event. Patients can be rechallenged with atezolizumab only after approval has been documented by both the investigator (or an appropriate delegate) and the principal investigator.

- 3. Biologic checkup, including a CBC with differential test, and liver and kidney function tests, including urinalysis, in addition to the blood work; if the patient is febrile, blood cultures should be considered as well.
- 4. Skin biopsies to assess for full-thickness epidermal necrosis, as is seen in SJS/TEN, as well as other possible etiologies like paraneoplastic pemphigus or other autoimmune blistering dermatoses or other drug reactions, such as acute generalized exanthematous pusulosis.
- 5. Consider following patients closely using serial clinical photography.
- 6. If mucous membrane involvement or blistering is observed on the skin, consider early admission to a burn center for further monitoring and management.
- 7. Review of systems: Skin pain (like a sunburn), fevers, malaise, myalgias, arthralgias, abdominal pain, ocular discomfort or photophobia, sores or discomfort in the nares, sores or discomfort in the oropharynx, odynophagia, hoarseness, dysuria, sores or discomfort in the vaginal area for women or involving the meatus of the penis for men, sores in the perianal area, or pain with bowel movements.
- 8. Physical examination: Include vital signs and a full skin examination specifically evaluating all skin surfaces and mucous membranes. Assess for lymphadenopathy, facial or distal extremity swelling (may be signs of DIHS/DRESS). Assess for pustules, blisters or erosions in addition to areas of "dusky erythema," which may feel painful to palpation. To assess for a positive Nikolsky sign, place a gloved finger tangentially over erythematous skin and apply friction parallel to the skin surface. Nikolsky sign is positive if this results in detached or sloughing epidermis demonstrating poor attachment of the epidermis to the dermis, which is the case in some autoimmune disorders (eg, pemphigus) and SJS/TEN.
- 9. Additional considerations: The usual prohibition of corticosteroids for SJS is not relevant here, as the underlying mechanism is a T-cell immunodirected toxicity. Adequate suppression is necessary with corticosteroids or other agents and may be prolonged in cases of DRESS/DIHS.

Grade 1		Not applicable. For SCARs, there is no G1 category; if lower BSA is involved with bullae or erosions, there should remain a high concern that this reaction will progress to G3 or G4.	
Other grades	Action taken on suspected IMP	Management with corticosteroids and/or other therapies	Monitor and follow up
Grade 2: Morbilliform "maculopapular") exanthem covering 10%- 30% BSA with systemic symptoms, lymphadenopat hy, or facial swelling	Withhold atezolizuma b	 Initiate therapy with topical emollients, oral antihistamines, and mediumto highstrength topical corticosteroids Consider initiation of prednisone (or equivalent) 0.5-1 mg/kg tapered over at least 4 weeks 	 Consider to refer patient to dermatologist Monitor patients closely every 3 days for progression to involvement of greater BSA and/or mucous membrane involvement. Consider following patients closely using serial photography Investigators are encouraged to contact experts in the management of immune toxicities of the ImmunoTOX network using the contacts details below.

			Patient can be rechallenged only after the sponsor and coordinating investigator approval
Grade 3: Skin sloughing covering , 10% BSA with mucosal involvement associated signs (eg, erythema, purpura, epidermal detachment, mucous membrane detachment)	Withhold atezolizumab *	 Treat skin with topical emollients and other petrolatum emollients, oral antihistamines, and high-strength topical corticosteroids; dimethicone may also be offered as an alternative to petrolatum Administer IV prednisolone (or equivalent) 0.5-1 mg/kg and convert to oral corticosteroids on response, wean over at least 4 weeks. Given the immune mechanism of action of Atezolizumab, use of immune suppression is warranted. Admit to burn and/or consult wound services with attention to supportive care, including fluid and electrolyte balance, minimizing insensible water losses, and preventing infection 	 Refer patient to dermatologist For mucous membrane involvement of SJS or TEN, appropriate consulting services should be offered to guide management in preventing sequelae from scarring (eg, ophthalmology; ear, nose, and throat; urology; gynecology; etc, as appropriate). Seek infectious disease consultation if patient might have secondary cellulitis or if patient has other infection risk factors, such as neutropenia Investigators are encouraged to contact experts in the management of immune toxicities of the ImmunoTOX network using the following contacts: Urgent advice: Contact directly the referent specialist of the ImmunoTOX network, [name] [contact] Half-urgent: Send email to the immunoTOX recommendation panel: [contact] and/or contact [name] [contact] Patient can be rechallenged only after the sponsor and coordinating investigator approval

Grade 4:
Skin erythema
and
blistering/slough
ing covering ≥
10% BSA with
associated
signs (eg,
erythema,
purpura,
epidermal
detachment,
mucous
membrane
detachment)
and/or systemic
symptoms and
concerning
associated
blood work
abnormalities
(eg, liver function test
elevations in the
setting of DRESS/DIHS)
ערבסט/טוחס)

- Permanently discontinue atezoluzuma
- Initiate IV (methyl)prednisolone (or equivalent) 1-2 mg/kg, tapering when toxicity resolves to normal
- IVIG or cyclosporine may also be considered in severe or corticosteroid unresponsive cases.
- Admit patient immediately to a burn unit or ICU with consulted dermatology and wound care services.
- Refer patient to dermatologist
- Consider further consultations based on management of mucosal surfaces (eg, ophthalmology; urology; gynecology; ear, nose, and throat surgery; etc).
- Consider pain/palliative consultation and/or admission in patients presenting with DRESS manifestations.
- Seek infectious disease consultation if patient might have secondary cellulitis or if patient has other infection risk factors, such as neutropenia
- Investigators are encouraged to contact experts in the management of immune toxicities of the ImmunoTOX network using the contacts details above

BSA = body surface area; CTCAE = Common Terminology Criteria for Adverse Events; DIHS = drug-induced hypersensitivity syndrome; DRESS = drug reaction with eosinophilia and systemic symptoms; G = grade; ICU = intensive care unit; irAE = immune-related adverse event; IV = intravenous; IVIG = intravenous immunoglobulin; NA = not applicable; SCAR = severe cutaneous adverse reactions; SJS = Stevens-Johnson syndrome; TENS = toxic epidermal necrolysis.

* For confirmed Stevens Johnson syndrome or toxic epidermal necrolysis, permanently discontinue atezolizumab. For other cases, resumption of Atezolizumab may be considered in patients who are deriving benefit and have fully recovered from the SCARs. Patients can be rechallenged only after approval has been documented by both the coordinating investigator and the referent specialist of the Immunotox network.

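### Section 5.3.2.9 gives two unreconciled sets of instructions for suspected SJS/TEN, which differ in Grade 3 starting steroid dose, atezolizumab action and rechallenge approvers

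*Protocol*

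**What the plan says.** Protocol section 5.3.2.9 contains two blocks that both reach SJS/TEN.

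**Block A, the dermatologic Table 8.** Rows for Grades 1 to 4 are followed by a row for SJS/TEN at any grade. That row withholds atezolizumab on suspicion, asks for specialist confirmation, and then says "Follow the applicable treatment and management guidelines above". It ends with permanent discontinuation if the diagnosis is confirmed. Among the rows above it:
- Grade 2 continues atezolizumab and mentions oral prednisone 0.5 mg/kg/day if topical steroids fail.
- Grade 3 withholds and reads "Initiate treatment with 10 mg/day oral prednisone or equivalent", raised to 1–2 mg/kg/day if there is no improvement in 48–72 hours. Atezolizumab restarts if the event resolves within 12 weeks.
- Grade 4 permanently discontinues and gives no steroid dose.

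Footnote c makes rechallenge depend on the investigator (or a delegate) and the principal investigator.

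**Block B, directly after Table 8.** It is headed "Severe Cutaneous Adverse Reactions (SCARs), including SJS, TEN, acute generalized exanthematous pustulosis and DRESS/DIHS General instructions".
- General instruction 1 is "Discontinue treatment and monitor closely for improvement, regardless of grade".
- Its own graded table withholds atezolizumab at Grades 2 and 3 and permanently discontinues at Grade 4.
- Its Grade 3 steroid line is "Administer IV prednisolone (or equivalent) 0.5-1 mg/kg and convert to oral corticosteroids on response". Its Grade 4 line gives 1–2 mg/kg intravenously.
- The Grade 2 and 3 rows add "Patient can be rechallenged only after the sponsor and coordinating investigator approval".
- The footnote first requires permanent discontinuation for confirmed SJS/TEN. For other cases it says "Patients can be rechallenged only after approval has been documented by both the coordinating investigator and the referent specialist of the Immunotox network".

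**The concern.** Neither block refers to the other, and no sentence says which one governs. The only pointer, in the Table 8 SJS/TEN row, sends the reader upward to the general rash rows and away from the SCAR table. A site that follows the protocol faithfully can therefore reach two different Grade 3 starting doses and routes for the same suspected reaction. It also cannot tell from the text whose approval is needed before atezolizumab is given again.

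Severe cutaneous reactions, with SJS and TEN as named examples, are adverse events of special interest in section 9.2.2 and must be reported immediately. General instruction 9 of the SCAR block itself treats adequate immunosuppression as necessary in these reactions, so by the protocol's own account a different starting dose is more than a formality. What is at stake is consistent handling of a life-threatening event across sites. No sample size, error rate or efficacy analysis is touched.

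**Working it through.** There is no statistical figure to reproduce. The check sets the two blocks side by side and converts the weight-based doses to milligrams.

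**Step 1. Side by side**

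| Item | Table 8, through its SJS/TEN row | SCAR block |
|---|---|---|
| Grade 2 systemic steroid | 0.5 mg/kg/day oral, considered if topical treatment fails | 0.5–1 mg/kg, to be considered |
| Grade 3 starting steroid | 10 mg/day oral | 0.5–1 mg/kg IV |
| Grade 3 if no improvement in 48–72 h | 1–2 mg/kg/day | not given |
| Grade 4 steroid | none stated | 1–2 mg/kg IV |
| Atezolizumab on suspicion | withhold (SJS/TEN row); continue (Grade 2 row reached by the back-reference) | discontinue (instruction 1); withhold (Grade 2 and 3 rows) |
| Atezolizumab at Grade 4 | permanently discontinue | permanently discontinue |
| Atezolizumab, confirmed SJS/TEN | permanently discontinue | permanently discontinue |
| Rechallenge approvers | investigator and principal investigator (footnote c) | sponsor and coordinating investigator (table); coordinating investigator and network specialist (footnote) |

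**Step 2. Grade 3 starting dose**

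Assumptions, none of them from the protocol: body weight 50–100 kg with 70 kg as the middle case; prednisone and prednisolone equal mg for mg, oral or IV; the SCAR dose is per day; the patient is Grade 3 on both scales.

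Ratio = (SCAR mg/kg × weight) ÷ 10 mg.
- 50 kg: 0.5 × 50 = 25 mg and 1 × 50 = 50 mg, so 2.5 to 5 times.
- 70 kg: 0.5 × 70 = 35 mg and 1 × 70 = 70 mg, so 3.5 to 7 times.
- 100 kg: 0.5 × 100 = 50 mg and 1 × 100 = 100 mg, so 5 to 10 times.

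**Step 3. How long the gap lasts**

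Table 8 escalates after 48–72 hours without improvement, which is 2 to 3 days. At 70 kg the escalated dose is 1 × 70 = 70 mg to 2 × 70 = 140 mg per day, against 35–70 mg in the SCAR row. In a patient who does not improve, the several-fold shortfall in Table 8 therefore covers the first 2 to 3 days. After that its range starts where the SCAR range ends.

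**Step 4. Other grades**

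At Grade 2 the ratio is 0.5–1 ÷ 0.5, which is 1 to 2 times, so the ranges touch. At Grade 4 no ratio exists because Table 8 states no dose.

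**Step 5. Approvers**

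There are three different pairs. Two of them are inside the SCAR block, so choosing that block as the governing one would not settle the matter.

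**The case against.** The best defence is that the two blocks agree where it matters most. Both permanently discontinue for confirmed SJS/TEN, both do so at Grade 4, and both withhold on suspicion in their specific rows. A reader might infer that a patient with confirmed SJS/TEN could return to atezolizumab under one table and not the other. The documents do not support that. A reader might also infer that Table 8 tells sites to keep dosing in suspected SJS/TEN. It does not: the SJS/TEN row says withhold in its own words, and the Grade 2 line enters only through a loosely worded back-reference.

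It can also be said that instruction 1 of the SCAR block does not say permanently, a word section 5.3.2 uses when it means it. Section 5.3.1 uses discontinue for a break in radiotherapy of a few days. So instruction 1 can be read as stopping for now, which matches withhold. That is a fair reading, but not one the text settles, since rechallenge is allowed two rows later.

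On dose, a reader might take the several-fold difference to hold at every grade and throughout treatment. Steps 3 and 4 show that it does not.

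Finally, the SCAR block is the more specific text and might be presumed to govern. That is a sensible presumption, but the Table 8 row points the other way and nothing in the section states the precedence. The three approval conditions could in principle all be met together, yet the protocol does not ask for that. All cohorts are closed to inclusions, so exposure is limited to patients still on treatment.

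**Conclusion.** The inconsistency is real but bounded.

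- **Dose.** For suspected SJS/TEN at Grade 3, the starting steroid dose differs by 3.5 to 7 times at an assumed 70 kg (2.5 to 10 times over 50–100 kg), and by route, for the first two to three days. At Grade 4 only one of the two blocks gives a dose.
- **Atezolizumab.** SCAR instruction 1 conflicts with the SCAR Grade 2 and 3 rows, and the Table 8 back-reference reaches a Grade 2 row that continues treatment.
- **Approvers.** Three pairs are named, and the SCAR table disagrees with its own footnote.

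The last two conflicts bear on suspected but unconfirmed cases and on other SCARs, because confirmed SJS/TEN and Grade 4 events are permanently discontinued in both blocks. The dose ratios rest on the assumptions listed with the calculation; the textual conflicts rest on none. No view is taken on which dose or rule is clinically right.

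**What to change.** In the next amendment, reconcile the dermatologic Table 8 (SJS/TEN row, the graded rows it points to, and footnote c) with the SCAR general instructions, table and footnote:
- State which block governs suspected SJS/TEN and other SCARs, and replace the upward reference in the Table 8 SJS/TEN row with a pointer to that block.
- Give one steroid instruction per grade for these reactions, so that the two blocks cannot be read as giving different starting doses.
- Give one atezolizumab instruction per grade, and say whether instruction 1 means a temporary or a permanent stop.
- Name one set of rechallenge approvers and use it in the table and the footnotes.

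The clinical content of each item is for the sponsor to decide. The cost is editing one subsection and telling the sites that still have patients on treatment.

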5.3.2.10 Neurologic Disorders

Myasthenia gravis and Guillain-Barre syndrome have been observed with single agent atezolizumab.

Patients may present with signs and symptoms of sensory and/or motor neuropathy. Diagnostic work-up is essential for an accurate characterization to differentiate between alternate etiologies. Myasthenia may be associated with myositis and patients should be managed accordingly. Management guidelines for neurologic disorders are provided in Table 11., with specific guidelines for myelitis provided in Table 12.

Table 9: Management Guidelines for Neurologic Disorder

Neurologic Disorder	Management
Grade 1	Continue atezolizumab.
Immune- related	Evaluate for alternate causes.
Neuropathy,	 Any cranial nerve disorder (including facial paresis) should be managed as per Grade 2 management guidelines below
	Withhold atezolizumab for up to 12 weeks after event onset.
	Investigate etiology and refer patient to a neurologist.
	Initiate treatment as per institutional guidelines.
	For general immune-mediated neuropathy
Grade 2 Immune- related Neuropathy, including facial paresis	 If event resolves to Grade 1 or better, resume atezolizumab. b If event does not resolve to Grade 1 or better while withholding atezolizumab, permanently discontinue atezolizumab and contact the Medical Monitor. c
	 For facial paresis: Initial observation OR initiate prednisone 1-2 mg/kg/day (if progressing from mild). Initiate treatment with gabapentin, pregabalin, or duloxetine for pain. If event resolves fully, resume atezolizumab. b If event does not resolve fully while withholding atezolizumab, permanently discontinue atezolizumab and contact the Medical Monitor. c
	•
Grade 3 or 4	 Permanently discontinue atezolizumab and the principal investigator ^c
Immune- related Neuropathy, including facial paresis	Refer patient to a neurologist
	 Treatment should be as per institutional guidelines and proceed as per Guillain-Barré syndrome management.

Myasthenia
Gravis and
Guillain-Barré
syndrome
(any grade)

- Permanently discontinue atezolizumab.and the principal investigator c
- · Refer patient to neurologist
- Initiate treatment as per institutional guidelines.
- Consider initiation of corticosteroids 1-2 mg/kg/day oral or intravenous prednisone
- Consider IVIG or plasmapheresis in patients with rapid progression with development of bulbar and/or respiratory symptoms.
- In life-threatening cases, consider IV methylprednisone 1 g/day for 3-5 days and consider other immunosuppressive agent. a
- a If corticosteroids have been initiated, they must be tapered over ≥ 1 month to ≤ 10 mg/day oral prednisone or equivalent before atezolizumab can be resumed.
- b Atezolizumab may be withheld for a period of time beyond 12 weeks to allow for corticosteroids to be reduced to ≤ 10 mg/day oral prednisone or equivalent. The acceptable length of the extended period of time must be agreed upon by the investigator and the Medical Monitor.
- c Resumption of atezolizumab may be considered in patients who are deriving benefit and have fully recovered from the immune-related event. Patients can be rechallenged with atezolizumab only after approval has been documented by both the investigator (or an appropriate delegate) and the principal investigator

Table 12 Management Guidelines for Immune-Mediated Myelitis

Event	Management	
Immune-mediated myelitis, Grade 1	Continue atezolizumab unless symptoms worsen or do not improve.	
	Investigate etiology and refer patient to neurologist.	
Immune-mediated myelitis, Grade 2	Permanently discontinue atezolizumab and contact the Medical Monitor.	
	Investigate etiology and refer patient to neurologist.	
	Rule out infection.	
	Initiate treatment with corticosteroids equivalent to 1 □ 2 mg/kg/day oral prednisone.	
Immune-mediated myelitis, Grade 3 and 4	Permanently discontinue atezolizumab and contact the Medical Monitor.	
	Initiate non-opioid treatment (e.g., pregabalin, gabapentin, duloxetine) for pain.	
	Hospitalize patient.	
	o Initiate treatment with corticosteroids equivalent to 1 g/day IV methylprednisolone.	
	o if event does not improve or there is worsening of symptoms within 3 days, consider IVIG or plasmapheresis and manage as per institutional guidelines.	
	Refer patient to a neurologist.	

IVIG: intravenous immunoglobulin.

